[contact] – a mixed-method, stepped-wedge, randomized controlled trial to assess a clinical pathway for home-dwelling people with dementia and their caregivers

Statistical Analysis Plan (SAP)

Version 17.01.2023

NFR Project number 273581

Introduction

Preface

The objective of the Statistical Analysis Plan (SAP) is to outline the statistical methodology to be used for the final analysis of [[contact]](#)[1].

The SAP is based on the following documents

Study Protocol	Version 4.0 (26.04.2019)
Amendments to Study Protocol / Observational Plan	Change in protocol due to Covid-19 restrictions. Approval for change from Regional Ethical Committee (REK: 10861, 06.04.2020), update clinicaltrials.gov (31.08.2020)
Scientific Review Committee Charter (SRC)	22.11.2017 Research Council Norway granted the [contact] allocation 19.06.2018 Date for signing the contract 06.05.2019 Approval Ethic Committee (2019/385/REK North)
Professional development Plan (PD)	Post-doc 1: 20210311 Post-doc 2: 20211209 Post-doc 3: 20201209
Statistical Analysis Plan for the Interim Analyses	Not applicable

Timing of statistical analyses

Final analysis after the last data collection period is completed.

Modification History

Changes to the study protocol

Protocol version 4.0 was changed in April 2020 due to the Covid-19 restrictions, as the pandemic severely hampered the implementation of the intervention which had to be delivered at the participants homes. We therefore had to change the design of the overall trial, postponing the intervention in two municipalities and delivering the intervention by phone in the last municipality. In addition, we initiated the PAN.DEM cohort in the [contact] trial, collecting data from phone interviews with caregivers on change in health service use and neuropsychiatric symptoms, risk perception and restrictions [2]. Changes in design approved by Ethical committee (REK: 10861), update on clinicaltrials.gov (31.08.2020)

Study Design

Indication	
Design	Stepped-wedge design

	Closed cohort where individuals are identified at the start of the trial and scheduled for repeated outcome assessment [3]
Phase	
Primary objective	To determine treatment effect on caregiver burden measured as Resource Utilization Dementia (RUD), and the Relative Stress Scale (RSS). Based on the correlation coefficient, we will use all three subcategories of RUD separately. Total score will be used when assessing RSS. Further, we will evaluate the economic consequences of the treatment by calculating Incremental Cost-Effectiveness Ratio (ICER) and quality adjusted life years (QALY).
Secondary objectives	To determine treatment effect on quality of life (QoL) using the European Quality of Life – 5 dimension – 5 levels (EQ-5D-5L), EQ-5D-VAS scale, Quality of Life in Alzheimer's disease scale (QoL-AD); neuropsychiatric symptoms in dementia using the Neuropsychiatric Inventory 12 item (NPI-12), agitation in dementia using Cohen-Mansfield Agitation Inventory (CMAI), depression in old age (Geriatric Depression Scale - GDS), functional level for instrumental and personal activities (ADL and IADL), and the caregiver rating of clinical meaningful change using Clinical Global Impression of Change (CGIC).
Exploratory objectives	
In line with total score of RSS, we will also explore the treatment effect on both single and clustered items.
 
In line with total score of QoL based instruments (EQ-5D-5L, QoL-AD, QoL – CG, GDS), we will also explore the treatment effect on both single and clustered items
 
To assess the effect on pain in dementia using the Mobilization – Observation – Behavior – Intensity Dementia Pain Scale (MOBID-2)
 
To determine the characteristics of the dyads who had the highest improvement in RUD and RSS, i.e., those who benefitted the most from the intervention.

Endpoints	
Primary endpoint: Change in caregiver burden and informal care time among the caregivers in the intervention group during active intervention period, and the follow-up. Change in Cost-efficiency of treatment.
 
Secondary endpoint: Improvement in QoL for both PwD and caregivers. Reduction in neuropsychiatric symptoms in dementia and functional level during active intervention period and follow-up.
 
Exploratory endpoint: Reduction in pain during active intervention period.

Treatments	Allocation to municipal coordinator delivering the multicomponent LIVE intervention (L:learning, I: innovation, V: volunteering and E:empowerment) or care as usual.
Number of patients	315 dyads will be screened to achieve at least 105 dyads per municipality.

Safety analysis	Not applicable
Planned enrolment	3 municipalities and 9 municipality districts

Sample size estimation

The required sample size calculated before recruitment of participants aimed to detect a difference of 7 h/week for the primary outcome RUD. Based on the literature[4], we assumed that the number of hours of informal care is 46 h/week with a standard deviation (SD) of 20 h/week. With 80% power and a significance level of 5%, the required sample size was estimated to be 260 dyads. To allow for 20% loss to follow-up, a total of 315 dyads, equaling 105 per municipality, must be included.

The post-hoc sample size calculations based on the outcome PADL showed that by treating the study as an individually randomized stepped wedge design[3], with 3 intervention sequences, 5 periods, effect size of 7h/week, outcome variance of 400, significance level of 5% and within-individual correlation of 0.1075 over the 24 month trial would require a total of 240 dyads to be included. To allow for 20% loss to follow-up, the sample size must reach 288 dyads.

Randomization, blinding and unblinding procedures

Block randomization was performed using a computerized random number generator to allocate individual dyads to the three intervention sequences. We will apply stratification to secure that about one third of the dyads in each treatment sequence will be recruited from each municipality. Research assistants, researchers conducting the analyses and other study personal conducting data collection will be blinded to the randomization order, the dyads will be blinded to group allocation until contacted by their coordinator at start of the intervention period. Given the practice change of the intervention, the municipality home care services and coordinators will be informed about allocation sequence when their clusters entered the intervention period.

Analysis Sets

Full Analysis Set (FAS)

The intention-to-treat population includes all randomized dyads who were assigned a coordinator by the municipality. The dyads will be analyzed separately (i.e., PwD and caregiver), dependent on outcome of interest.

This will be the primary analysis set for baseline summary statistics of demographics, primary, secondary and exploratory efficacy analysis as elaborated in section 10.

Municipal coordinator set (MCS)

All coordinators in all municipality districts

Usage overview of analysis sets table

Analyses	FAS	MCS	
Disposition			
Demographics and background	x		
Medical history			
Efficacy: primary	x		
Efficacy: secondary	x		x
Efficacy: other	x	x	x

General Statistical Methods and Definitions

General statistical methods

The statistical analysis will be presented by treatment group for the different analysis sets as outlined in section 4.

Stepped wedge design (SWD) do not strictly feature a treatment and control group, and thus, the summary statistics will include all participants at baseline, and the characteristics according to intervention sequences.

Continuous variables will be summarized using descriptive statistics (means and interquartile ranges), and categorical variables will be presented by frequencies and percentages. A table will present the number of caregivers and PwD with the following data: missing values, mean, median, standard deviation and confidence intervals.

Means and median as well as percentages will be presented with 1 additional decimal place and standard deviation by 2 additional decimals.

If the number of PwD or caregivers in a category is 0, then percentage will not be displayed.

P-values will be reported to 3 decimal places.

Unless otherwise specified, all statistical tests will be two-sided.

Causal model

Due to the longitudinal structure of the collected trial data, we considered the following linear mixed model to estimate and identify the treatment effect due to the intervention. Our SWD, consisting of $j = 3$ municipalities and 3 steps, is a closed cohort design, and thus, time related confounders are important to adjust for [5] when assessing treatment effect.

Mixed-effects regression is one of the most common approaches when estimating the intervention effect in SWD [6, 7]. In our design, we will consider the following model as our primary analysis model, assuming a constant treatment effect.

$$(1) Y_{ijt} = \beta_0 + O_{ijt}\beta_1 + X_{ijt}\beta_2 + b_i + \epsilon_{ijt}$$

where notation Y_{ijt} refers to the primary outcome caregiver burden (RUD and RSS), elaborated in section 3 Study Design, for individual i nested in municipality j at time point t . O_{ijt} is the treatment indicator (effect of receiving assistance from a municipality coordinator) and β_1 is the average treatment effect parameter of interest. Since the study collects repeated observations from the same participants, we consider a longitudinal regression model that adjusts for participant-level random effect, $b_i \sim N(0, \sigma_b^2)$, which corresponds to a compound symmetric correlation structure.

$\epsilon_{ijt} \sim N(0, \sigma_\epsilon^2)$ represents random error that changes across t and i .

X_{ijt} constitutes control variables which are demographic, socio-economic and clinical confounders (age, sex, caregiver marital status, work status, ADL function), and stratification variables used in the design stage.

Due to the non-normal distribution of hours and costs we will use both linear mixed-effects, as well as general lineal mixed regression model for assessing both primary variables. For RSS, and other continuous variables, we use Linear Mixed regression model. Log-transformation of the outcome will also be considered to address potential non-normality in the response.

Intervention effect

In secondary analysis, we will further examine the extent to which the treatment effect will depend on the calendar time when COVID lockdown happened, and the potential for delayed effect. We collectively refer these effects as heterogeneous treatment effect, and provide a schematic illustration following Section 3.2 of Li et al. (2020) [6]. The rationale is that there the lockdown during the pandemic may contribute to change in the intervention effect. In addition, the intervention may be most effective when it is first introduced, and the sustained effect may be smaller. Therefore, when modelling the intervention effect, we will allow for heterogeneous effect and assess the robustness of our primary analysis. The table below shows how the intervention effect can differ between periods (t) across different groups (g). The deltas (δ) constitute the intervention effect, and their subscript defines heterogeneous effects where δ_0 is the pre-lockdown intervention effect, δ_0^* is the intervention effect post-lockdown, and δ_1^* is the follow-up post-lockdown treatment effect.

When modelling the intervention effect, we will test the null-hypothesis (H_0)

$$\delta_0 = \delta_0^* = \delta_1^*$$

	$t = 1$	$t = 2$	$t = 3$	$t = 4$
$g = 3$			δ_0^*	δ_1^*
$g = 2$		δ_0^*	δ_1^*	δ_1^*
$g = 1$	δ_0	δ_1^*	δ_1^*	δ_1^*

Economic evaluation

If we identify an average treatment effect on one of the primary and secondary outcomes, we will use cost-efficiency (CEA) and cost-utility analysis (CUA) to evaluate the economic effects of the LIVE treatment.

In cost-effectiveness analysis the effect is measured in health units (or other outcome measures depending on the context). The outcomes are common health measures in natural units, and the results are presented as cost per effect unit/outcome measure. In cost-utility analysis, also called cost per QALY analysis, the effect is measured as quality-adjusted life years (QALYs) on a scale of 0 (death) and 1 (full health). A quality-adjusted life year (QALY) captures both life years gained and improved health as a result of treatment [8, 9].

The economic evaluation will be measured at society level.

Costs and QALYs will be measured for each phase of 6 months

The cost-effective analysis will relate the difference in total mean costs at societal level per 6 months between all intervention -and usual care phases to the difference in RUD, RSS, QoLs, QALYs, NPI, function level such as ADL and IADL

The analysis will use a discounting rate at 3.5%.

Following other costs studies calculating RUD in an advanced economy setting, our analysis will use 35% of the Norwegian average income to value lost leisure time for retired caregiver.

The primary economic evaluation will use the opportunity cost method to assess the costs of informal caregiving. For a sensitivity analysis, the replacement cost will be used.

Unit costs will be based on information from Statistics Norway and information from the primary health care institutions in each municipalities.

Covariates and strata

In the main statistical analyses, the following covariates are used for both caregivers and PwD.

For PwD: Age, sex, marital status, cohabitation status, number of co-caregivers, clinical characteristics of dementia (dementia etiology, neuropsychiatric symptoms, functional level)

For Caregivers: Age, sex, marital status, cohabitation status, numbers of co-caregivers involved in caregiving for the PwD, work status, use of health care services,

Groups, municipalities

Municipalities will be grouped in the main analysis and used as an adjustment variable (fixed effects). This is not the case for district municipalities as we consider that the dyads are similar within municipalities

Subgroups

In subgroup analyses, the following covariates will be used to define relevant subgroups:

- Gender (male, female)
- Work (retired and working caregivers)
- Caregiver relation (spouse, children)
- Residency (living alone, or with caregiver)
- Formal caregiver (whether dyads are receiving care by home nursing)
- Categories of caregiver burden intensity
- Categories of dementia diagnoses

Results from subgroups will be presented for the primary analyses.

Observation and analysis times

Study periods

Timeline															
Groups/participants	Inclusion period	Control group			Kristiansand 3, N=35			Bærum 3, N=35			Bergen 3, N=35				
					Kristiansand 2, N=35										
					Bærum 2, N=35										
					Bergen 2, N=35										
		Kristiansand 1, N=35						Follow up							
Number of months		0	1 2	3 4	5 6	7 8	9 10	11 12	13 14	15 16	17 18	19 20	21 22	23 24	
Date		01.09 2019		01.03 2020		01.09 2020		01.03 2021							

		STUDY PERIOD							
		Enrollment		Allocation	Post-allocation				Close-out
TIMEPOINT	-t	0		t1	t2	t3	t4	t5	
ENROLLMENT:									
Eligibilityscreen	x								
Informed consent	x								
Allocation		x							
INTERVENTIONS:									
1st group			x	x					
2nd group				x	x				
3rd group					x	x			
ASSESSMENTS:									
Baseline variables			x						
Outcome variables				x	x	x	x	x	

The stepped wedge randomized control design. A) The randomization in time takes place at month 0. First group (red) is in the intervention period from month 1 to 6, second group (yellow) from month 7 to 12, third group (green) from month 13 to 18. Implementation seminars will be held at month 0, 6 and 12, midway evaluation at month 3, 9 and 15. Data will be collected at baseline (month 0), after first intervention period (month 6-7), after second intervention period (month 12-13), after third intervention period (month 18-19) and at end of study at 24 months. B) Schedule of enrollment, interventions and assessments over the study period.

Demographics and Background Characteristics

Demographics and baseline characteristics

The following demographic characteristics will be presented descriptively and listed for both PwD and caregiver:

- Sex (male, female)
- Age in years
- Marital status (spouse, child)
- Work status (employed, unemployed, retired)
- Number of co-caregivers
- MMSE total score
- RUD (number of care hours the last 30 days)
- RSS total score
- NPI total score
- QoL total score

Date of informed consent and protocol version will be listed

Medical history

We will provide information on the number of years since formal diagnosis of dementia together with descriptive statistics.

Exposure and Compliance

Treatment groups

The definition of treatment assignment as specified in section “Analysis sets” will be used in this section, too.

Deviations from the randomized treatment sequence occurred under the first Covid-19 lockdown, see section Modification History, Changes to the study protocol

Treatment duration

Each municipal coordinators are writing logs, and we will collect the data and calculate total hours of care by the coordinator, divided into different categories.

Descriptive statistics for the total hours of care by the coordinators will be presented.

Delivery of the intervention

One coordinator from the municipal per dyad

Efficacy

Primary efficacy analysis

The primary efficacy analysis variable caregiver burden is based on two variables. The first is RUD, divided in three categories: number of hours the last 30 days invested in personal, instrumental and supervisory care. The second is RSS measured as total score but also

specific and clustered items. Lower hours of informal care as well as lower score of RSS, indicates reduction in caregiver burden.

The null hypothesis states that there are no differences in burden and resource utilization between the LIVE intervention and usual care. The primary alternative hypothesis (H1) states that the LIVE intervention will improve caregiver burden and resource utilization compared with usual care. The secondary alternative hypothesis (H2) is that the LIVE intervention will provide more cost-efficient services than usual care.

H0: LIVE treatment = control

H1: LIVE treatment > control

H2: cost efficiency > control

where LIVE treatment denotes the proportion of caregivers experiencing improvement in care burden. The primary hypothesis will be statistically assessed by means of a χ^2 test on the one-sided significance level of 2.5% (corresponding to 5% two-sided).

We will plot the regression line to visualize the parallel effect for both treatment group and control group.

The significance level will be set to 2.5% (one-sided, corresponding to 5% two-sided), the corresponding level of one-sided CI is 97.5% (corresponding to 95% two-sided).

Missing data

We will pre-specify a list of baseline covariates that are likely associated with the missingness and the outcome, and adjust for these covariates in our primary analyses. This covariate-adjusted analysis will be valid under the missing at random (MAR) mechanism.

Sensitivity and robustness tests of regression analyses and economic evaluation

Due to the complexity of setting up a causal model in a stepped-wedge design trial, we will run several robustness and sensitivity analyses for primary and secondary efficacy analyses.

Subgroup analyses (demographic and clinical) will be performed and compared with the primary efficacy analysis

Robustness checks will also be performed using clustered or single items on measurements such as NPI, RSS, GDS and QoL.

In the economic evaluation, we will set up a simulation model where we can test different cost levels. We will plot the resulting ICERs graphically as a ratio between costs and the effectiveness/utility or as a distribution with uncertainty in cost / effectiveness plane. Four quadrants represent all combinations of possible outcomes. The more effective outcomes are located right on the x-axis, and with the rise of y-axis the cost of the outcome rises. An ICER

that is more costly and more efficient than care as usual is located in the first quadrant; in case of a more costly and less efficient treatment, ICER is in second quadrant.

Secondary efficacy analyses

Other efficacy analyses will be based on the secondary objectives (QoL measurements and NPI) for both PwDs and caregivers. They will be analyzed on the full analyses set (FAS). Higher scores of QoL (for both EQ-5D-5L and QoL Alzheimer's disease scale) indicates low burden for both PwDs and caregivers. Further, high total scores of NPI indicate high burden for both PwDs and caregivers.

Interim analysis

An interim analysis is not planned.

Software

If not stated otherwise, the data will be analyzed using Stata version 17

Abbreviations

CG – Caregiver

FAS – Full Analysis Set

PwD – Person with dementia

RUD – Resource Utilization Dementia

SD – Standard Deviation

SWD – Stepped Wedge Design

QoL – Quality of Life

MI – Multiple Imputation

MAR – Missing at Random

MNAR – Missing not at Random

References

1. Husebo, B.S., et al., *[contact] the clinical pathway for home-dwelling people with dementia and their caregivers: study protocol for a mixed-method, stepped-wedge, randomized controlled trial*. Trials, 2020. **21**(1): p. 510.

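### The stated power is for undivided informal-care hours, but the primary analysis tests three RUD categories separately, and the only category-level calculation reuses the undivided-hours effect and variance

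*SAP*

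**What the plan says.** **Sizing before recruitment.** Under Sample size estimation, the calculation "aimed to detect a difference of 7 h/week for the primary outcome RUD". Its inputs are for hours of informal care taken as a whole: "we assumed that the number of hours of informal care is 46 h/week with a standard deviation (SD) of 20 h/week". The result: "With 80% power and a significance level of 5%, the required sample size was estimated to be 260 dyads". Dropout is then added: "To allow for 20% loss to follow-up, a total of 315 dyads, equaling 105 per municipality, must be included".

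**Post-hoc sizing.** The same section adds a second calculation, introduced as "The post-hoc sample size calculations based on the outcome PADL". It treats the trial as an individually randomized stepped wedge with 3 sequences and 5 periods. Its inputs are an effect of 7 h/week, a variance of 400 and a within-individual correlation of 0.1075, and it gives 240 dyads. It states no power.

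**Analysis.** The primary objective under Study Design says "Based on the correlation coefficient, we will use all three subcategories of RUD separately". In the next sentence it keeps the total score for RSS. Under Primary efficacy analysis, RUD is divided into "number of hours the last 30 days invested in personal, instrumental and supervisory care". Neither section names a RUD total as a primary variable. The SAP gives no mean, SD or target effect for any single category, and no value, source or rule for the correlation.

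**The concern.** A power statement belongs to one outcome with one effect and one variance. Here the effect and variance describe informal care as a whole, while the tests are run on its parts. A reduction of the planned size, spread over three categories, is smaller in each of them, and the variance falls by an amount the SAP does not give. A reader who takes 80% as the power of each primary RUD test has no basis for it.

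The PADL calculation looks like the missing category-level sizing, because PADL is apparently the personal-care category. But it changes the label of the outcome and leaves the numbers as they were. The units also differ: the sizing is in h/week and the analysis in hours per 30 days. At stake is how the results are read. A non-significant category could be taken as evidence against an effect that the trial had 80% power to find.

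**Working it through.** **1. Reproduce the plan's figure.** Inputs from Sample size estimation: difference 7, SD 20, power 80%. Level from Primary efficacy analysis: "The significance level will be set to 2.5% (one-sided, corresponding to 5% two-sided". The SAP does not state the allocation for this calculation; I assume two equal parallel groups.

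n per arm = 2 × 400 × (1.960 + 0.842)² / 7² = 128.1, so 129 per arm and 258 in total, against the stated 260.

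Power at 130 per arm = Φ(7/20 × √65 − 1.96) = Φ(2.822 − 1.960) = 80.6%.

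So 260 follows from the undivided-hours inputs.

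**2. Compare the PADL inputs.** Effect: 7 h/week in both calculations. Variance: 400 = 20², the same SD. Write undivided hours as T = P + R, with P personal care and R the other two categories.
- Equal effects on T and P require a net effect of zero on R.
- Equal variances require Var(R) + 2 Cov(P, R) = 0. Either R hardly varies, or it is negatively correlated with P by just the amount needed.
- In relative terms, 7/46 = 15% of undivided hours. If personal care were one third of them (assumed; 15.3 h/week), 7/15.3 = 46%.

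The SAP offers no support for any of these conditions.

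**3. Power per category, as an illustration.** The SAP gives no category figures. Assume an equal split of the effect, 7/3 = 2.33 h/week; equal category variances; a common correlation r; and an SD of 20 for the sum. Then 400 = 3σ²(1 + 2r), so σ = √(400 / (3(1 + 2r))), and power at 260 dyads = Φ(2.33/σ × √65 − 1.96).

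| r | σ | 2.33/σ | power |
|---|---|---|---|
| 0 | 11.5 | 0.202 | 37% |
| 0.3 | 9.1 | 0.256 | 54% |
| 0.5 | 8.2 | 0.286 | 63% |
| undivided hours | 20 | 0.350 | 80.6% |

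The range is wide. At a one-third share, power is 80.6% if the SD shrinks in full proportion to 6.67 (r = 1), and 15% if the SD stays at 20 as in the PADL calculation.

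**4. The same illustration in the stepped wedge.** Generalised least squares with fixed period effects, compound symmetry, correlation 0.1075, variance 400, 3 sequences, 5 periods and follow-up counted as treated gives a standard error of 1.94 h/week at 240 dyads. Power for undivided hours = Φ(7/1.94 − 1.96) = Φ(3.604 − 1.960) = 95%. Multiplying 3.604 by (2.33/σ)/0.35 gives power per category of 55%, 75% and 84% for r = 0, 0.3 and 0.5. Under this model 80% power needs 145 dyads and 90% needs 194.

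**5. Units.** The factor is 30/7. In hours per 30 days the sizing inputs are a difference of 30, a mean of 197 and an SD of 86.

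**The case against.** The strongest reply is that the SAP does size on an analysed outcome. PADL is by label one of the three categories, and a post-hoc effect and variance for it cannot be shown to be wrong from this document. That stands in part: it would be wrong to say that every calculation in the SAP concerns an outcome that is not analysed. What remains is that the PADL inputs are identical to the undivided-hours inputs and are not justified, and that two categories have no calculation.

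Second, per-category power is not the power to find something. Under the assumptions of step 3, with test statistics correlated as the outcomes are, the chance that at least one category is significant at 260 dyads is 75%, 84% or 86%, against 81% for undivided hours. So a reader should not infer that the split makes a missed effect much more likely overall. Those figures carry no multiplicity correction; with Bonferroni over three they fall to 53%, 67% and 72%.

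Third, a reader might infer that the SAP replaced an earlier primary total, or picked categories by their correlation. The document supports neither. The protocol is not at hand, and all three categories are kept, so the correlation is a reason for splitting and not for selecting. That its value and rule are absent is a reporting gap.

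Fourth, that the 46 h/week covers exactly personal, instrumental and supervisory care is an inference. The SAP says only hours of informal care and takes the figure from a cited study.

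Finally, a family-wise error of 14% for three tests (1 − 0.95³) assumes independence and counts both directions, whereas the SAP sets 2.5% one-sided. Multiplicity is a separate question and is not part of this point.

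**Conclusion.** The concern holds in a limited form. The 260/315 sizing reproduces for undivided informal-care hours, and the stated 80% power belongs to that outcome. It does not apply to the personal, instrumental and supervisory hours that the primary analysis tests. The PADL calculation does not close the gap, because the same effect and variance can describe both the whole and one part only under conditions that the SAP does not claim.

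The size of the loss cannot be fixed from the document. Power of 37% to 63% per category at 260 dyads, and 55% to 84% in the stepped wedge at 240, rests on the assumed equal split of effect and variance and on correlations from 0 to 0.5. It does not show that the trial is underpowered: if the effect fell mostly in one category, or the categories were almost perfectly correlated, the loss would be small or absent. The finding is that power for the RUD endpoints as analysed has not been established.

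**What to change.** - State under Sample size estimation that the 80% power at 260 dyads and the post-hoc 240 dyads both refer to undivided informal-care hours, and confirm which kinds of care the 46 h/week covers.
- Relabel the post-hoc calculation accordingly, or redo it with a PADL-specific effect and variance. Either way, state its power.
- Give the resulting power for personal, instrumental and supervisory hours, each with its assumed mean, SD and target effect, in one unit (h/week or hours per 30 days).
- State the correlation behind the split, its source and the rule applied.
- Report total RUD hours (personal + instrumental + supervisory) with the same model, so that an effect of the planned size is also tested on the outcome the trial was sized for. Whether the total or the three categories is primary is the sponsor's choice. Promoting a total in a SAP of this date would itself be a late change, to be explained if made.

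The cost is SAP wording and one extra analysis of items already collected. The downside is a less favourable stated power per category.

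### An exploratory objective treats the largest observed improvement as the largest benefit, although selecting on change favours dyads with high starting values even with no treatment effect

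*SAP*

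**What the plan says.** The last exploratory objective in the Study Design table is to determine the characteristics of the "dyads who had the highest improvement in RUD and RSS, i.e., those who benefitted the most from the intervention". The second half of that phrase makes observed improvement and benefit the same thing. The SAP names no pair of visits, cut-off, control-period comparison, baseline adjustment or interaction test for this objective.

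Other parts of the SAP bear on it:

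- Causal model: "we will consider the following model as our primary analysis model, assuming a constant treatment effect". Equation (1) has a participant random intercept and one treatment coefficient. The text calls adjustment for time-related confounding important, but the equation and its covariate list show no explicit period term.
- Intervention effect: the heterogeneity to be modelled concerns lockdown timing and delayed effect, not dyad characteristics.
- Subgroups: gender, work, caregiver relation, residency, home nursing, burden category and dementia diagnosis are listed, with results for the primary analyses. No interaction test is stated, and the list is not linked to this objective.
- Study periods: all three groups receive the intervention in turn, with data collected at baseline, after each of three intervention periods and at 24 months.
- Sample size estimation: "we assumed that the number of hours of informal care is 46 h/week with a standard deviation (SD) of 20 h/week". The post-hoc calculation, based on PADL, uses "outcome variance of 400" and "within-individual correlation of 0.1075 over the 24 month trial".

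**The concern.** A dyad's untreated course is never observed alongside its treated course. Its change from control to intervention therefore contains any treatment effect, any calendar-time trend (including lockdown) and the dyad's own variation, whether measurement noise or real fluctuation. Dyads with the largest falls in care hours or stress score will tend to be those whose starting value was high, because a high starting value regresses towards the mean.

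A profile of such dyads would show high baseline burden whether or not the intervention works. It would then be reported, in the SAP's own terms, as a profile of who benefits. Under equation (1), with one constant effect, no dyad benefits more than another, so differences in change can reflect only covariates, time and residual variation.

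**Working it through.** **Reproducing the plan's figure.** The inputs are a difference of 7 h/week, SD 20, 80% power and two-sided 5% (Sample size estimation). Per arm: 2 × (1.96 + 0.84)² × 400 / 49, rounded up, = 129, so 258 in total. The SAP states 260, so the inputs are understood correctly.

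**Illustration with no treatment effect.** Take two measurements per dyad, normally distributed, SD 20, correlation ρ, with no treatment effect and no time trend. The top quarter is chosen here only to give a size; the SAP sets no cut-off.

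- SD of change = 20 × √(2(1 − ρ)). At ρ = 0.1075: 20 × √(2 × 0.8925) = 26.7 h/week.
- Mean improvement in the top quarter = SD of change × φ(0.674)/0.25 = 26.7 × 1.271 = 34.0 h/week, about five times the 7 h/week target (34.0/7 = 4.9).
- Correlation of baseline with improvement = √((1 − ρ)/2) = √(0.8925/2) = 0.67.
- Baseline excess of the top quarter over the overall mean = 20 × 0.668 × 1.271 = 17.0 h/week.

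Only ρ = 0.1075 comes from the SAP; the other values are assumed.

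| ρ | SD of change | Top-quarter mean improvement | Top-quarter baseline excess | Share improving ≥ 7 h/week |
|---|---|---|---|---|
| 0.1075 | 26.7 | 34.0 | 17.0 | 39.7% |
| 0.3 | 23.7 | 30.1 | 15.0 | 38.4% |
| 0.5 | 20.0 | 25.4 | 12.7 | 36.3% |
| 0.7 | 15.5 | 19.7 | 9.8 | 32.6% |
| 0.9 | 8.9 | 11.4 | 5.7 | 21.7% |

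A simulation with 260 dyads and 4,000 replicates agrees. At ρ = 0.1075 the top quarter improved by 33.9 h/week and had started 22.5 h/week above the remaining dyads. That baseline difference was nominally significant in every replicate.

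**Averaging periods.** There are five assessments. Suppose change is the mean of control assessments minus the mean of later ones, with equal correlation between visits as in equation (1).

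- First sequence (1 control, 4 later): SD = 20 × √(0.8925 × (1 + 1/4)) = 21.1; top quarter 21.1 × 1.271 ≈ 27 h/week.
- Second and third sequences (2 and 3, or 3 and 2): SD = 20 × √(0.8925 × (1/2 + 1/3)) = 17.2; top quarter ≈ 22 h/week.

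The artefact shrinks but remains three to four times the target.

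**Checking the obvious remedy.** Adding a treatment-by-baseline-RUD interaction to the mixed model does not work if the baseline visit is also an outcome. Baseline is always a control-period value, so regression to the mean loads onto the interaction. A null simulation (261 dyads, 3 sequences, 5 periods, SD 20, period effects, random intercept, 60 replicates) gave mean spurious interactions of −0.45, −0.27 and −0.10 h per hour of baseline at ρ = 0.1075, 0.5 and 0.8. These were significant in 100%, 100% and 93% of replicates. A second run of 30 replicates at each value gave −0.45, −0.26 and −0.11, all significant. The bias vanished when baseline was dropped as an outcome or a baseline-by-period term was added. It did not appear for a separate baseline covariate.

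**The case against.** The strongest reply is that the SAP states an aim and no method. A reader might infer that dyads will be ranked on a two-visit change score and a top fraction declared responders. The document does not say so; the top quarter and the two-visit change are illustrations. This stands and limits the size claim. It does not rescue the wording, because the objective itself defines benefit as observed improvement, and any selection on observed change has the same defect.

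The inputs are also weak. The correlation comes from a post-hoc calculation on PADL, the SAP expects non-normal hours, RUD is analysed in three subcategories over 30 days, and RSS has no SD or correlation. Hence the range. Regression to the mean does not depend on normality, and the baseline correlation formula is scale-free, but ρ for RSS would have to be assumed.

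A reader might also infer from 0.1075 that nearly all change is noise. That does not follow: one minus the correlation is the within-dyad share of outcome variance, and some of it may be real change over 24 months.

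Finally, the planned subgroups already cover most relevant characteristics. That is true. The gap is that no interaction test is stated and this objective is not tied to them.

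**Conclusion.** The definition is invalid as stated, and nothing else in the SAP corrects it. With no treatment effect, selecting on observed improvement would still yield a high-baseline group that seems to benefit. Under the SAP's SD and PADL-based correlation, the apparent top-quarter improvement is about 34 h/week on two measurements, or 22 to 27 with averaged periods. At assumed correlations of 0.5 and 0.9, the two-measurement figure is about 25 and 11. These sizes assume normality, no time trend and a top-quarter cut chosen here.

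The point is minor. It concerns one exploratory objective with no hypothesis attached, and a reader should not infer that the primary result is at risk. Nor does the SAP say that the profile would decide who is offered a coordinator.

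**What to change.** Delete the clause that equates improvement with benefit. State that the objective will be answered by treatment-by-characteristic interactions, reported as estimates with intervals, in the mixed model with period effects written into the equation. Use the listed subgroup variables at their pre-treatment values: gender, work, caregiver relation, residency, home nursing and diagnosis.

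If baseline RUD, RSS or burden category is used as a moderator, either drop the baseline visit from the outcome vector or add a baseline-by-period term, and say which.

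The cost is a few sentences and some extra model terms. Interaction estimates will have wider intervals than a responder comparison, which is the main drawback.
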